8.1 Screening Assessments and Procedures

8.1.1 Informed Consent

Informed consent must be obtained according to the Informed Consent Process described in Section 11.2.

8.1.2 Demographic Variables

Demographic variables will include items such as age, sex, ethnicity, body mass index, and race.

8.1.3 Medical/Surgical/ COPD/ and Smoking History

A history of relevant current or past medical conditions, surgical history, COPD history, and smoking history (current or former [yes or no]) will be obtained.

- Minor surgical procedures (eg, tonsillectomy, appendectomy) performed more than 5 years prior to Screening Visit 0 do not need to be recorded.
- COPD history will include COPD exacerbation history and COPD type (emphysema and/or chronic bronchitis), as assessed by the investigator or medical professional). Chronic bronchitis is defined as “regular production of sputum for three or more months in two consecutive years (in the absence of other conditions that may explain it [GOLD, 2020]).”
- Former smokers are defined as those who have stopped smoking for at least 6 months prior to Screening Visit 0.

Medical and COPD condition(s) identified during the Screening Visit will be documented as medical history and not as an AE(s) unless the condition worsens during the study and meets the definition of an AE.

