4.0 STUDY DESIGN

4.1 Overall Design

RPL554-CO-302 is a multicenter, randomized, double blind, parallel group, placebo controlled study to determine the efficacy and safety of ensifentrine 3 mg twice daily (BID) for 24 weeks administered via nebulizer vs. placebo in patients 40 to 80 years of age with moderate to severe COPD (FEV₁ 30% – 70% of predicted, FEV₁/forced vital capacity (FVC) ratio <0.7, with documented COPD symptoms).

Up to 50% of patients recruited will be using stable background maintenance as *either* long-acting muscarinic antagonist (LAMA) *or* long-acting β 2 agonist (LABA) maintenance therapy for 24 weeks and all patients will be provided with rescue albuterol/salbutamol for use as needed during the study. Up to 20% of patients are allowed to take inhaled corticosteroids during the study under certain provisions (see Sections 6.7.2 and 6.7.3). Washout of patients on stable background maintenance LAMA or LABA monotherapy for the sole purpose of study eligibility is not recommended.

Randomization will be stratified by two different factors: stable background maintenance LAMA or LABA therapy use (yes or no) and cigarette smoking (current or former). Patients will be randomized 5:3 to receive ensifentrine (3 mg):placebo for 24 weeks. Patients in the background maintenance LAMA or LABA therapy stratum must withhold Twice-Daily maintenance LAMA or LABA (or LAMA/ICS or LABA/ICS) for 24 hours and Once-Daily maintenance LAMA or LABA (or LAMA/ICS or LABA/ICS) for 48 hours prior to initiation of any spirometry. All patients must withhold short acting bronchodilator (SABA) rescue medication for at least 4 hours prior to initiation of any spirometry.

All sites will use standardized spirometry and ECG equipment provided by a central vendor and all spirometry and ECGs will be over-read by the blinded central vendor.

Patients will be screened for eligibility before entering a 28-day run-in period to ensure a stable background maintenance LAMA or LABA bronchodilator medication regimen and to collect baseline information on symptoms and rescue medication use. Permitted rescue and background medications and the condition of their use during the study are described in Section 6.7.2. Prohibited medications and the prohibited time intervals prior to Screening are described in Section 6.7.3

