The proportion of responders on the SGRQ, patients with an improvement of at least 4 units, will be compared between treatment groups using a logistic regression model with fixed factors treatment, region, and background medication strata, and smoking status. Imputation of missing data will be done similar as for continuous endpoints. A sensitivity analysis will be performed in which patients with missing data at the required visit will be considered non-responder in the analysis.

The time to first COPD exacerbation during the 24 or 48 week treatment period, depending on stratification, will be visualized using a Kaplan-Meier plot and compared between treatment groups using the log-rank test, stratified by region, background medication strata, and smoking status. As a secondary evaluation a Cox's proportional

hazards model will be used with the same factors. Patients without exacerbations will be censored at last day in the treatment period, including period of recording after possible treatment withdrawal. The treatment difference in the Cox model will be expressed as a hazard ratio. Assumption of proportional hazards will be checked. The number of COPD exacerbations during the 24- or 48-week treatment period will be compared between treatments using a negative binomial model adjusting for treatment, region, background medication strata and smoking status and further using the log exposure time as an offset. The treatment difference from the negative binomial model will be expressed as an annualized risk ratio.

Subgroup analyses will be performed for the primary endpoint and selected secondary endpoints by gender, age-class (below or above 65 years), region, background medication strata, smoking status, ICS use, known chronic bronchitis, and FEV₁ reversibility at baseline ($\geq 12\%$ and ≥ 200 mL).

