7. STATISTICAL CONSIDERATIONS

7.1.ADJUSTMENTS FOR COVARIATES AND FACTORS TO BE INCLUDED IN ANALYSES

The following covariates and factors are used in the analyses. For details of their inclusion in the models, see the specific analysis section.

- Fixed effects: treatment (ensifentrine, placebo), region (Europe, North America), visit (Day 1, Week 6, Week 12, Week 18, Week 24), visit*treatment, stable background maintenance of LABA or LAMA (or LAMA/ICS or LABA/ICS) therapy use (yes, no), cigarette smoking (current, former)

- Random effect: patient
- Covariate: baseline

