16.3.3. ANALYSIS OF OTHER EFFICACY VARIABLES

Change from baseline to average FEV₁ AUC_{6-12h} will be analyzed using ANCOVA approach and missing data will be imputed using imputation, as described in sections 16.1.3 and 16.2.2.1 of the SAP, respectively.

[figure not shown]
Model assumptions will be tested and solved, if failed, as per section 16.1.3 of the SAP.

The number of moderate or severe COPD exacerbations will be analyzed using a negative binomial model adjusting for treatment, region, actual background medication strata and actual smoking strata, as well as using log study time (years) as an offset. For study time, Visit 5 will be taken into account for completer patients, and End of Study visit or last contact date for withdrawal patients. The treatment difference from the negative binomial model will be expressed as an annualized risk ratio. The data will also be summarized by treatment group over duration of the study period.

Time to first moderate or severe COPD exacerbation during the study period will be presented as per following:

- Primary approach: Analyzed using the log-rank test, stratified by region, actual background medication strata and actual smoking strata. Summary of number of patients with events and number of patients censored will be summarized. Outcome visualized using a Kaplan-Meier plot.
- Sensitivity analysis: Analyzed using Cox proportional hazards Regression model stratified by region, background medication strata and smoking strata. Patients without exacerbations will be censored at last day in the treatment period, including period of recording after possible treatment withdrawal. The treatment difference in the Cox model will be expressed as a hazard ratio.

Testing proportional hazard assumptions:

1. Check that the covariates are independent of each other through proc phreg in SAS software.
2. Check that the hazard (hazard ratio) is independent of time through $\log(-\log(\text{survival}))$ vs $\log(\text{time})$ plot and an interaction test for treatment times $\log(\text{time})$.

The health index and VAS score for EQ-5D-5L questionnaire will be analyzed using ANCOVA approach, as described in section 16.1.3 of the SAP, with data imputation described in section 16.2.2.3 of the SAP.

HRU over 24 weeks will be summarized for each event and for overall count.

Analysis for the genetics data is described in section 18 of the SAP.

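### Exacerbation history is collected at Screening but is not a covariate in the negative binomial model for exacerbations or an item in the SAP baseline list; adding it is a small, cheap gain in precision

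*Protocol*

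**What the plan says.** Protocol 8.1.3, on Screening history, states that "COPD history will include COPD exacerbation history and COPD type (emphysema and/or chronic bronchitis"). It gives no look-back period and does not say whether a count or a yes/no answer is recorded.

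The exacerbation analyses do not use this item:

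- **Rate.** SAP 16.3.3 specifies a "negative binomial model adjusting for treatment, region, actual background medication strata and actual smoking strata", with log study time as offset. Protocol 9.4.1 has the matching "negative binomial model adjusting for treatment, region, background medication strata and smoking status".
- **Time to first event, main approach.** SAP 16.3.3: "Analyzed using the log-rank test, stratified by region, actual background medication strata and actual smoking strata". Protocol 9.4.1 also has the log-rank test "stratified by region, background medication strata, and smoking status".
- **Time to first event, sensitivity.** SAP 16.3.3: "Analyzed using Cox proportional hazards Regression model stratified by region, background medication strata and smoking strata".

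History is also absent from the general covariate list in SAP 7.1 ("The following covariates and factors are used in the analyses"), the subgroups in SAP 7.5 and the baseline characteristics in SAP Section 10. It plays no part in allocation. Protocol 4.1 states that "Randomization will be stratified by two different factors", namely background LAMA or LABA use and smoking.

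Exacerbation frequency and time to first exacerbation are Other Endpoints (protocol 3.2.3, SAP 16.3). They lie outside the seven-step hierarchy of SAP 7.4 and carry no stated power.

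**The concern.** The exacerbation model departs from the SAP's own practice. Elsewhere each outcome is adjusted for its own baseline: FEV₁ in the primary ANCOVA (16.1.3), BDI for TDI (16.2.3.1), SGRQ total score in the SGRQ responder model (16.2.3.2), and baseline E-RS and trough FEV₁ in their responder models (16.3.3). For SGRQ responders the SAP added the baseline score although protocol 9.4.1 had not listed it. The exacerbation model has no such term, although the natural counterpart is collected.

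The two items recorded together in protocol 8.1.3 also part ways. Chronic bronchitis and emphysema reach the baseline table, and chronic bronchitis is a subgroup. Exacerbation history is not mentioned again.

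At stake is a little precision in the rate ratio. In addition, a reader of the listed baseline summaries could not judge whether the arms were alike on prior exacerbations.

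**Working it through.** **The plan's own figure.** The only power statement concerns FEV₁ AUC0-12h (protocol 9.2). SE = 250 × √(1/500 + 1/300) = 18.26 mL; 59/18.26 = 3.232; power = Φ(3.232 − 1.960) = 89.8%, against 90% stated. It reproduces, but has no bearing on exacerbations.

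**Inputs.** From the documents: 500 vs 300 patients, and 24 weeks, so t = 168/365.25 = 0.460 years. Assumed, because the documents give none: placebo rate 0.2 to 1.0 per year; dispersion k 0.5 to 1.0; 25% to 40% with a prior exacerbation; their rate 1.5 to 3 times that of the others; treatment rate ratio 0.7; full follow-up. Region, background therapy and smoking are left out of the calculation.

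**Formulas.**
- Without history: V = (1/μ₁ + k*)/500 + (1/μ₀ + k*)/300, where k* = k + (1 + k)·CV² and CV² is the between-patient variation in rate due to history.
- With history: compute V within each history stratum using k, then combine as 1/Σ(1/V).

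**Middle case** (rate 0.4, k = 0.5, 25% with history, history ratio 2).
- μ₀ = 0.4 × 0.460 = 0.1840; μ₁ = 0.7 × 0.1840 = 0.1288.
- Relative rates are 0.8 (no history) and 1.6 (history), so CV² = 0.75 × 0.64 + 0.25 × 2.56 − 1 = 0.12 and k* = 0.5 + 1.5 × 0.12 = 0.68.
- Without history: V = (7.765 + 0.68)/500 + (5.435 + 0.68)/300 = 0.03727; SE 0.1931.
- With history: stratum variances are 0.05963 (375 vs 225) and 0.09478 (125 vs 75); V = 1/(16.77 + 10.55) = 0.03660; SE 0.1913.
- The SE falls by 0.9% and the variance by 1.8%, worth 800 × (0.03727/0.03660 − 1) ≈ 15 patients.

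**Across the range** (percentages from unrounded values):

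| Rate/yr | k | With history | History ratio | SE without | SE with | Fall in SE | Power, without to with |
|---|---|---|---|---|---|---|---|
| 0.2 | 0.5 | 25% | 1.5 | 0.2651 | 0.2647 | 0.1% | 27.0% to 27.0% |
| 0.4 | 0.5 | 25% | 2 | 0.1931 | 0.1913 | 0.9% | 45.5% to 46.2% |
| 0.6 | 1.0 | 25% | 3 | 0.1770 | 0.1706 | 3.6% | 52.2% to 55.2% |
| 1.0 | 1.0 | 25% | 3 | 0.1495 | 0.1413 | 5.5% | 66.5% to 71.4% |

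A separate simulation (about 250 trials per scenario; 27% with history, history ratio 2 to 3, placebo rate 0.4 to 0.8, k = 0.8, true rate ratio 0.65, 20% early exit) gave falls of 0.7% (0.2111 to 0.2096) to 3.5% (0.1631 to 0.1574).

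**Chance imbalance.** The SD of the arm difference in history prevalence at 25% is √(0.25 × 0.75 × (1/500 + 1/300)) = 0.032; at 40% it is 0.036. The shift in the log rate ratio is about SD × (ratio − 1)/(1 + p(ratio − 1)), with p the prevalence. For p = 25% and ratio 2 this is 0.0316/1.25 = 0.025, a factor of 1.026. For ratio 3 it is 0.0632/1.5 = 0.042, a factor of 1.043; for ratio 1.5 the factor is 1.014. In the middle case the shift is 0.025/0.193 = 0.13 of a standard error. At 1.96 SD the factor is 1.03 to 1.09 across the range. Simulated type I error without adjustment was 4% to 6%.

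**Cox model** (500 simulated trials per scenario). Adding history left the SE of the log hazard ratio unchanged: 0.1964 vs 0.1966, and 0.1665 vs 0.1667 in a strong case. The mean log hazard ratio moved away from zero (−0.328 to −0.332; −0.318 to −0.328), and power rose by about 1 to 3 points.

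**The case against.** The planned model is defensible. It is prespecified and adjusts for region and both randomisation factors, and the endpoint is exploratory. The gain is small, and in the middle case power barely moves. Every input to its size is assumed. Eligibility narrows recent history by excluding steroid-treated exacerbations within 3 months of Screening, COPD hospitalisations within 12 weeks, and exacerbations between Screening and randomisation. The covariate has no stated look-back period or format. Output content is set in a shells document (SAP Section 8) that is not available here, and SAP Section 21 does not name history among the data left unsummarised. It may therefore be tabulated somewhere; what can be said is that it is not in the Section 10 list.

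All of this stands, and it keeps the point minor. It does not remove it: the item is collected, the SAP adjusts other outcomes for their own baseline, and the change is cheap.

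A reader might infer more than the documents support:

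- **That the rate comparison is biased or its error rate inflated.** Chance imbalance is random error that the interval and p-value already allow for.
- **That the hazard ratio is also less precise than it could be.** Adjustment does not shrink its SE; it yields a conditional hazard ratio with slightly more power.
- **That post-bronchodilator FEV₁ % predicted should be added too.** No gain has been computed for it, and eligibility restricts it to 30% to 70%.
- **That the pooled analysis with study 301 has the same gap.** It has its own SAP (SAP Section 1), which is not available here.

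**Conclusion.** The point holds as a minor efficiency improvement on an exploratory endpoint. Exacerbation history is collected, is not a covariate in the negative binomial model and is not in the Section 10 baseline list. With adjustment the SE of the log rate ratio would be about 0.1% to 5.5% lower. A one-SD imbalance in history would no longer move the estimate by the 3% to 4% expected if prior exacerbators have two to three times the rate (1.4% at a ratio of 1.5).

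These sizes rest wholly on assumed rate, dispersion, prevalence and prognostic strength. They also leave out the three factors already in the model, which may absorb part of the gain. No planned conclusion is shown to depend on the omission.

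**What to change.** Before unblinding:

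1. In SAP 16.3.3, add exacerbation history at Screening as a covariate in the negative binomial model, for example none vs one or more. Define the look-back period and coding from what the eCRF holds, and state how a missing history is handled. Record the change from protocol 9.4.1 in SAP 3.3.
2. Add exacerbation history by treatment group to the SAP Section 10 baseline table. This is worth doing whatever the modelling gain.
3. Optionally, add the same term to the sensitivity Cox model and label the result a conditional hazard ratio.
4. Leave the stratified log-rank test unchanged.
5. Consider the same term in the separate pooled SAP; this is only a suggestion.

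The cost is SAP wording, one model term and one table row on data already collected, plus the work of defining the covariate. Timing matters, because a covariate chosen after the results are known would be less credible.

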8.1.4 Prior/Concomitant Medications/Therapies

A history of prior medications used will be obtained and recorded as described in Section 6.7.4.

8.1.5 Vital Signs

Vital signs will be completed at Screening per the instructions in Section 8.4.1. In addition, height in centimeters (cm), weight in kilograms (kg), and body mass index will also be measured and recorded at Screening.

8.1.6 Electrocardiogram

12-Lead ECGs will be completed per the instructions in Section 8.4.2.

8.1.7 Chest X-Ray

A CXR (posterior-anterior) will be obtained at Screening or obtained within 12 months prior to Screening. If a CXR within the past 12 months is not available but a CT scan within the same time period is available, the CT scan can be reviewed in place of a CXR.

For subjects in Germany, if a CXR or CT scan is not available in the 12 months prior to Screening, the subject is not eligible for the study, as this assessment will not be conducted at the Screening visit.

8.1.8 Spirometry Assessment

Spirometry at Screening will be completed per the instructions in Section 8.3.1.

8.1.9 Modified Medical Research Council Dyspnea Scale

The mMRC dyspnea scale is a questionnaire that measures COPD symptoms and defines symptom burden at Screening (Fletcher, 1960). Site staff will administer/interview the patient to complete the mMRC dyspnea scale questionnaire.

8.1.10 Clinical Laboratory Assessments

Clinical laboratory tests will be conducted per the instructions in Section 8.4.3. Abnormal chemistry and/or hematology may be repeated during Screening/Run-in.

8.1.10.1 Viral Serology

Viral serology for HBsAg, anti-HBc, anti-HBs, and Hepatitis C Virus will be obtained at Screening. Chronic stable hepatitis B and C is not exclusionary if the patient otherwise meets study entry criteria.

8.1.10.2 COVID-19

Testing for COVID-19 may optionally be completed (Section 11.3) prior to spirometry and following local requirements. Patients with a positive COVID-19 test result indicating an active infection at Screening or anytime between Screening and Randomization will be excluded.

Patients with a positive COVID-19 antibody test from a past exposure who do not exhibit symptoms of an active COVID-19 infection are eligible to participate in the study.

8.1.11 Physical Examination

A complete physical examination will include, at a minimum, assessments of the Cardiovascular, Respiratory, Gastrointestinal, and Neurological systems.

Investigators should pay special attention to clinical signs to ensure patients have had no previous serious illness(es).

8.1.12 Inclusion/Exclusion Criteria

Patient eligibility will be assessed using the inclusion criteria (Section 5.1) and exclusion criteria (Section 5.2).

8.1.13 Electronic Diary Activities

Electronic Diary training will be conducted and the eDiary will be issued for use during the study. Patients will be instructed to enter their daily symptoms (E-RS:COPD/EXACT-PRO questionnaire), rescue medication (puffs per day), and maintenance LAMA or LABA medication (if applicable) into the eDiary each day.

8.1.14 Interactive Response Technology

Patients will be registered in the IRT system (See Section 8.5.2).

8.1.15 Nebulizer Equipment Training

See Section 8.5.5 for details on nebulizer equipment training. At the Screening Visit, site staff will review the information and instructions provided by the manufacturer with the patient (e.g. Instructions for Use, located in the Pharmacy Manual). Hands-on training with the nebulizer equipment will not occur until the Randomization Visit.

8.1.16 Dispense Rescue Medication

Rescue medication (albuterol/salbutamol) will be dispensed for use as needed during the study but must be withheld for at least 4 hours prior to spirometry and should be withheld for at least 4 hours prior to ECGs. See Section 6.7.2 for additional details.

8.2 Randomization Criteria Assessment– Day 1

The criteria for Randomization are described in Section 5.3.

8.3 Efficacy Assessments

Planned timepoints for all efficacy assessments are provided in the SoA (Section 1.3).

8.3.1 Spirometry

Spirometry will be obtained using spirometry equipment provided by the central spirometry vendor that meets or exceeds the American Thoracic Society minimal performance recommendations [Miller, 2005].

The central spirometry vendor will provide a spirometry manual with additional instructions and details.

All Spirometry will be reviewed and over-read by the central spirometry vendor and the spirometry vendors determination of acceptable endpoint measurements will override determination by the investigative site.

- Acceptable spirometry efforts should have a satisfactory start of test and end of test (plateau in the volume-time curve) and be free from artifacts due to cough, early termination, poor effort, obstructed mouthpiece, equipment malfunction, or other reason [Miller, 2005].
- For FEV₁ and FVC determinations, at least 3 but no more than 8 acceptable spirometry efforts should be obtained.
- The largest FEV₁ and FVC from the 3 acceptable efforts should be recorded, even if they do not come from the same effort.

8.3.1.1 Spirometry Training

Prior to the first spirometry measurement at each clinic visit requiring Spirometry, the site staff will train each patient on how to perform acceptable spirometry maneuvers according to instructions provided by the central spirometry vendor.

8.3.1.2 Spirometry must be performed as follows:

- **Coordination of the timing of spirometry and in-clinic dosing with blinded study medication is critical. See Section 1.4, for the Schedule of Spirometry and In-Clinic Dosing with Blinded Study Medication.**
- Spirometry Start Time: between 06:00 am and 10:00 am.
- Health Outcomes: Complete health outcome assessments as described in Section 8.3.3 prior to spirometry.
- Withhold the Following or Reschedule the Visit*:
 - *Blinded Study Medication*: Blinded study medication must be withheld until pre-dose spirometry is completed.
 - *Rescue Medication*: Albuterol/salbutamol must be withheld for ≥ 4 hours.
 - *Maintenance LAMA or LABA medications (or LAMA/ICS or LABA/ICS, if applicable)*: Must withhold Twice-Daily medications for 24 hours and Once-Daily medications for 48 hours prior to spirometry.

****If the withholding periods above are not met, the visit should be rescheduled to be held within 3 days of the scheduled visit.***

- Recommendation/ Request: Patients should refrain from smoking and/or caffeinated beverages prior to Spirometry and ECGs for the withholding periods below:
 - *Smoking*: No smoking for at least 1-hour prior to each spirometry assessment.
 - *Caffeinated Beverages*: Abstain from drinking beverages with high levels of caffeine (eg, tea, coffee) for 2 hours prior to each spirometry assessment.

